Does your study involve the exposure to radiation, radiotracers and/or radiological imaging modalities?

Yes

No (If No, no RRSC review is needed)

Will any of the radiation exposure result from procedures that are or could be performed solely as a result of a subject's participation in the research protocol?

Yes

No

The following are examples of procedures involving ionizing radiation:

(Refer to [appendix 17.3](#) for radiotracers, radiation use and [17.5 for nuclear medicine](#) guidance and language)

- [X-rays \(examples: CT scan, chest x-ray, hand/wrist x-ray, abdomen x-ray, DEXA, pQCT, Fluoroscopy/Angiography\)](#)
- [Nuclear Medicine scans \(examples: FDG-PET, PET/CT, Tc-99m, SPECT, MUGA, bone scan\)](#)

If you are unsure please contact [name] in EHRS ([contact]).

Ultrasound

Yes

No

Will your study be using CT Scans? (CACTIS is the appropriate contact for studies involving CT scans)

Yes

No

Check off all of the following procedures that will be performed in your research- each option you select will link to the template language document:

- [Apheresis/plasma exchange](#)
- [Leukapheresis](#)
- [Bone Marrow Biopsy or Aspirate](#)
- [Use of AP clinical specimens](#)
- [Biopsies- check those which apply](#)

[Blood draw](#)

a. Screening

- Informed Consent
- Questionnaires
- Two weeks of prospective assessment with sleep diaries
- PCP assent
- Home Sleep Apnea Testing (HSAT, type 3 or 4 sleep study)

b. Study Intervention Phase

See section 3.0 – Investigation Plan.

c. Rescue Therapy [if applicable] N/A

d. Unscheduled Visits

All subjects may contact the study coordinator at any time by email or phone to make an appointment or to discuss questions or concerns.

e. Subject Withdrawal

Subjects may withdraw from the study at any time without impact to their care. They may also be discontinued from the study at the discretion of the Investigator for lack of adherence to intervention or study procedures or visit schedules, AEs, or due to medication use. The Investigator or the Sponsor (if applicable) may also withdraw subjects who violate the study plan, or to protect the subject for reasons of safety or for administrative reasons. It will be documented whether or not each subject completes the clinical study. Subjects who withdraw early will have one final visit to collect investigational product and to follow up regarding adverse events.

i. Data Collection and Follow-up for Withdrawn Subjects

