"Subjects who withdraw consent to participate in the study will be asked to return their foil packs. Please see section 5g".

f. Early Termination Visits

See section; Subject Withdrawal

g. Subject Contact

Subjects will be contacted through phone, email, and via HIPAA compliant Zoom. Identifying information, such as names, will not be used.

Axsome Study - Table of Instruments						
Instrument Name	Abbreviation	Pre	Daily	Weekly	Post	Follow-up (3 mo.)
Sleep Disorder Symptom Checklist	SDS-CL-25	X			X	
Insomnia Severity Index	ISI	X		X	X	X
Retrospective Sleep Continuity Assessment Questionnaire	RSQAQ					X
Daily Sleep Diary	DSD		X			
Epworth Sleepiness Scale	ESS	X		X	X	
Brief Fatigue Inventory	BFI	X		X	X	
Functional Assessment of Chronic Illness Therapy – Fatigue Scale	FACIT-F	X		X	X	
PROMIS-SF 7a	PROMIS	X		X	X	
Functional Outcomes of Sleep Questionnaire	FOSQ-10	X				X
Profile of Mood State Questionnaire	POMS	X				X
Patient Health Questionnaire	PHQ-9	X		X	X	
Medical Symptom Checklist	MSCL	X		X	X	
Morin Insomnia Treatment Acceptability Scale	MITAS					X
Ecological Momentary Assessment	EMA		X			
Psychomotor Vigilance Test	PVT		X			

9. Study Evaluations, Measurements, and Schedule

a. Medical Record Review N/A

b. Physical Examination N/A. Physician Assent will be ascertained.

c. Vital Signs N/A. Physician Assent will be ascertained.

d. Laboratory Evaluations

The primary lab evaluation at screening is the Home Sleep Apnea Testing (HSAT, type 3 or 4 sleep study).

e. Pregnancy Testing

An effective method of birth control (as determined by their physician and intake) is required for women who are pre-menopausal. There are no requirements regarding the specific form of contraception that must be used. Subjects must agree to continue to use this method of birth control during the entire course of the study. If a subject does become pregnant during the study, they will be disenrolled. Outcome data on incidental pregnancies will not be collected.

f. Other Evaluations, Measures N/A

g. Efficacy Evaluations

The primary efficacy evaluation is accomplished with on-line prospective sampling, e.g., daily sleep diaries and the completion of weekly questionnaires.

h. Pharmacokinetic Evaluation N/A

i. Genetic Testing (only if applicable) N/A

j. Safety Evaluations

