As noted above, side effects will be assessed in several ways: daily assessments via the sleep diaries and weekly evaluation with a medical symptom checklist (52 symptoms where positive endorsements allow subjects to rate their average severity and number of days affected).

10. Statistical Plan

k. Primary Endpoint

The primary endpoint is total wake time (time spent awake in bed) at the end of post-treatment, as measured via a web based self-report Sleep Diary.

I. Secondary Endpoints

1. Patients treated with CBT-I will have significantly greater improvements in sleep continuity from baseline to post-treatment compared to patients not administered CBT-I.
2. Patients treated with CBT-I in combination with solriamfetol will have significantly greater improvements in sleep continuity from baseline to post-treatment compared to patients treated with CBT-I alone.
3. Exploratory hypotheses: Patients treated with CBT-I in combination with solriamfetol will have significantly greater adherence with sleep restriction (i.e., sleep rescheduling, prescribed time to bed [PTTB]) and on daytime performance measures (e.g., ESS, FSS, etc.) compared to CBT-I alone.

m. Sample Size and Power Determination

To detect a clinically significant difference in self-reported total wake time of 30 minutes between the four treatment groups at the end of post-treatment using an ANOVA test, this study will require 10 subjects per group x 4 groups = 40 treatment completers. These calculations assume a standard deviation in total wake time of 19 minutes, with 80% power to detect the clinically significant change at an alpha level of .05. A total of 60 subjects will be recruited to obtain a sample of 40 subjects that complete the study due to attrition.

n. Statistical Methods

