Primary analyses will be conducted on an intention to treat basis and the trial conducted and reported according to CONSORT guidelines. Variable distributions will be examined to investigate homoscedasticity, outliers and normality, and corrected where appropriate using data transformations. The primary analysis is a 4(condition: +/- solriamfetol and +/- CBT-I) x 2(time: pre- and post-treatment) mixed ANOVA on absolute and percent change in total wake time ([TWT], time spent awake per night). If the interaction between condition and time is significant, Dunnett multiple comparisons will be conducted to further investigate differences in TWT between active treatment conditions versus the control condition to test Hypotheses 1-3. These analyses will be unadjusted in the first instance and then adjusted for covariates (primarily, age and sex).

An interim unadjusted analysis as per above will be conducted after 50% of the target sample have completed post-treatment (i.e., when N=20).

Secondary analyses include examining the interaction between treatment condition and time on other outcomes, including sleep continuity assessed via Sleep Diary (SL, WASO, EMA, TST, SE), insomnia (ISI), daytime sleepiness (ESS and KSS), fatigue (FSS and modified KSS), and daytime function (FOSQ-10, POMS, and PVT). Additionally, compliance to the medication (adherence to daily pill administration, as assessed via blister packs) and to sleep restriction (adherence to prescribed time to bed) will be investigated as covariates.

i. Baseline Data

Baseline and demographic characteristics will be summarized by standard descriptive statistics (including mean and standard deviation for continuous variables such as age and standard percentages for categorical variables such as gender).

ii. Pharmacokinetic Analysis **N/A**

iii. Interim Analysis **N/A**

iv. Safety Analysis

Side effects and adverse events will be assessed in several ways: daily assessments via the sleep diaries, and with a weekly evaluation using a medical symptoms checklist (52 symptoms where positive endorsements allow subjects to rate their average severity and number of days affected),

An adverse event will be defined as 1) any behavioral or health complaint spontaneously reported during the study, 2) an above threshold score on the study clinical assessment instruments (ESS, PHQ-9, or GAD-7), and/or a 20% increase in the medical symptom check list scores (frequency or severity).

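### Section 8.e lets participants be removed from the study for non-adherence with no provision for later sleep diaries, so post-treatment total wake time may be missing selectively; the likely bias is small and the remedy is cheap

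*Combined protocol and SAP*

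**What the plan says.** Section 8.e lists grounds on which a participant may be "discontinued from the study at the discretion of the Investigator for lack of adherence to intervention or study procedures or visit schedules". Adverse events and medication use are also grounds. The next sentence says that the investigator or sponsor "may also withdraw subjects who violate the study plan".

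On what follows an early exit, section 8.e says: "Subjects who withdraw early will have one final visit to collect investigational product and to follow up regarding adverse events". Section 8.e.i, whose heading concerns data collection and follow-up for withdrawn subjects, says only this: "Subjects who withdraw consent to participate in the study will be asked to return their foil packs". Section 12.x (Confidentiality) adds an attempt to obtain permission to collect at least vital status, but only for people who revoke authorisation to use their health information.

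The primary endpoint (section 10.k) is diary-reported TWT at the end of post-treatment. Section 10.n says: "Primary analyses will be conducted on an intention to treat basis". The primary model is a "mixed ANOVA on absolute and percent change in total wake time". If the condition-by-time interaction is significant, "Dunnett multiple comparisons will be conducted to further investigate differences in TWT between active treatment conditions versus the control condition". Section 10.o names all-randomized, all-treated and protocol-compliant populations. No method for missing TWT is given.

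**The concern.** An intention-to-treat analysis needs outcomes from everyone randomised, including those who do not adhere. Section 8.e permits the investigator to end the participation of the people who adhere least, and the protocol does not say that their diaries continue. Someone removed in this way may contribute no post-treatment TWT. The people who matter here are those who miss capsules, sessions or prescribed bedtimes but could still complete a web diary. Someone removed for not completing diaries was not supplying TWT anyway.

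The exposure differs by contrast:

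- **CBT-I versus no CBT-I.** No sham is described. CBT-I adds 8 weekly sessions and a prescribed time to bed, so these arms offer more ways to be judged non-adherent, and allocation is known to those making the judgement.
- **CBT-I plus solriamfetol versus CBT-I alone, and the solriamfetol contrast for which the study is powered (section 5.6).** The drug is masked. CBT-I demands are the same in the two CBT-I arms. Differential removal can arise only if the drug itself changes who leaves.
- **The exploratory outcome of "significantly greater adherence with sleep restriction".** Removing the least adherent truncates this measure in both CBT-I arms.

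The Publication Plan gives the primary intent as obtaining effect size data, so bias in an estimate matters even where no test result would change.

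**Working it through.** **Does any text supply the missing diaries?** The final visit in section 8.e covers product return and adverse events. It is my reading that this sentence also governs removals by the investigator. Section 8.e.i covers foil packs after withdrawn consent. Section 12.x covers vital status after revoked authorisation. Sections 4 and 6.d set a general schedule for all subjects of 2 weeks before, 8 weeks during and 2 weeks after treatment, and section 8 says that all subjects complete daily diaries. Neither statement addresses people who have been removed. The finding is therefore silence: later diaries are neither provided for nor forbidden.

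**The plan's sample size (section 10.m).** The inputs are a 30-minute difference, SD 19 minutes, alpha 0.05, 80% power and four groups of 10. With means of 0, 15, 15 and 30, the noncentrality is 10 × (15² + 0 + 0 + 15²)/19² = 12.47. The F(3, 36) test then has 81.1% power at 10 per group and 75.8% at 9, so 10 per group is reproduced. Recruiting 60 to complete 40 implies attrition of 20/60 = 33%, not split by reason or arm.

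**Precision of one contrast.** I take 19 minutes as the SD of the analysed change, which is exact if the pre-post correlation is 0.5 (assumption). For 10 versus 10, SE = 19 × √(2/10) = 8.50 minutes.

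**Bias.** Let f be the share of an arm removed and d the gap in mean TWT change between those removed and those retained. The retained mean is shifted by f × d, and the bias in a contrast is f1·d1 − f0·d0. The documents give neither quantity. To keep d plausible, I assume removal of the lowest fraction f on a latent normal adherence score that has correlation ρ with TWT change. The shift is then ρ × 19 × φ(z_f)/(1 − f), where z_f is the normal quantile at f and φ the normal density.

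At ρ = 0.5:

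- f = 20%: 0.5 × 19 × 0.280/0.80 = 3.32 minutes (implied d = 3.32/0.20 = 16.6)
- f = 10%: 0.5 × 19 × 0.1755/0.90 = 1.85 minutes (implied d = 1.85/0.10 = 18.5)
- Bias: 3.32 − 1.85 = 1.47, about 1.5 minutes

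| ρ (assumed) | Bias, 20% versus 10% removed |
|---|---|
| 0.3 | 0.9 min |
| 0.5 | 1.5 min |
| 0.7 | 2.1 min |

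The 1.5-minute figure is 1.5/8.50 = 0.18 of an SE, 1.5/30 = 5% of the target difference and 1.5/19 = 0.08 SD. If those removed slept better than those retained, the sign reverses. Equal removal gives zero bias only if the gaps are also equal: 20% in both arms with gaps of 30 and 15 minutes gives 0.20 × 30 − 0.20 × 15 = 3 minutes.

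**Effect on a test.** For a two-sided 5% Dunnett procedure with three comparisons and 36 df, the critical value is 2.45. With no true effect, the false-positive rate of one comparison is 1.9% with no bias, 2.1% at 1.5 minutes and 2.6% at 3 minutes. Requiring a significant omnibus test first lowers these to about 1.3%, 1.5% and 1.9%.

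**The case against.** The strongest reply is that the harm is conditional at every step and negligible in size. The clause is permissive and sets no threshold or expected number of removals. The protocol has other responses to non-adherence: management within CBT-I sessions and changes of dose timing. It checks diary compliance before enrolment and pays for completed diaries. It plans to examine adherence as a covariate, which anticipates keeping people whose adherence varies. A bias of 1.5 minutes lies far inside a 95% half-width of about 17 minutes (2.03 × 8.50). All of this stands, and it is why the point is minor. It does not close the gap, because naming an all-randomized population does not supply its outcomes.

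A reader might infer three stronger things that the documents do not support:

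- **That error rates could be badly inflated.** Removal of 33% versus 0% with a 30-minute gap gives 0.33 × 30 = 9.9 minutes and a per-comparison rate of about 11%. That assigns one arm a removal rate equal to the whole planned attrition and the other arm none. Under the selection model it also needs a correlation of about 0.96. A 30-minute gap needs about 0.90 even at 20% removal, and 0.81 at 10%. This case deserves no weight.
- **That unmasking threatens every comparison.** It can drive differential removal only where CBT-I is compared with no CBT-I.
- **That the protocol stops diaries after removal.** It does not say so.

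**Conclusion.** The point holds as a cheap improvement, with medium confidence. The rule permits removal from the study on post-randomisation behaviour, and no text secures the primary outcome afterwards, contrary to the intention-to-treat principle in section 10.n. Under moderate assumptions the bias is about 1 to 2 minutes in a contrast of CBT-I with no CBT-I. This rests on assumed removal shares, an assumed link between adherence and TWT, and SD 19 for the change. The number who would be removed is unknown and may be small.

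It would be wrong to conclude that the powered solriamfetol comparison is compromised. Masking leaves only drug-related differences in exit. That route is not empty, since the plan hypothesises that solriamfetol improves adherence alongside CBT-I, but nothing in the documents shows it to be large. I have put no size on the truncation of the exploratory adherence outcome.

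**What to change.** In section 8.e, separate stopping capsules or CBT-I from leaving the study, and state that non-adherence alone does not end data collection. Ask every randomised participant who has not withdrawn consent to continue the existing web diary through post-treatment. In section 10.n, state that these participants are analysed as randomised. Exclude non-adherers only from the protocol-compliant population already named in section 10.o. The primary model need not change for this purpose.

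The cost is a few sentences, with no new instrument. The downside is some incomplete diaries after stopping and possibly a less favourable effect estimate. There is also a small gain in precision: one more participant kept in each arm (11 rather than 10) lowers the SE from 8.50 to 19 × √(2/11) = 8.10 minutes.

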5.1 Screening

Participants with insomnia will be recruited via established recruitment approaches. Advertising includes social media strategies, which have been found to be maximally productive (e.g., Google and Facebook Ads where the catchment is limited to within 60 miles of Philadelphia). Potential participants will be provided with contact information and a link to our screening page (www.sleeplessinphilly.com), which has proved successful in past studies. The study CRC and/or PI will review the screening form and contact the participant via e-mail to let them know whether or not they pass this screening stage. If so, participants will provide physician assent to confirm eligibility. If they are eligible, the CRC and/or the PI will follow-up with the participant via HIPAA compliant telehealth to complete the consent and provide more information about the study.

Please note that the intake questionnaires to be used include a set of measures that are validated and a set of measures that are specific to our laboratory. Subjects that are still eligible after the intake interview will be instructed to obtain their PCP's assent to participate in the study.

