Use of medication expressly for the purpose of falling or staying asleep (e.g., trazadone/ desyrel, melatonin, Tylenol PM, Nyquil, Benadryl).

Assessed with patient Hx

While medication can be used while participating in CBT-I, it is recommended that medications taken for sleep be discontinued.

Night shift work

Assessed with patient Hx

To ensure enrolled subjects are on a normal sleep schedule

Compromised renal function

Assessed with patient Hx

Will ascertain physician assent

To ensure the safety of the subject as Solriamfetol has been found to be contraindicated in those with renal impairment.

Use of MAOIs

Assessed with patient Hx
Will ascertain physician assent
To ensure safety as MAOIs are contraindicated with the concurrent use of solriamfetol

Major Coronary Artery Disease and/or uncontrolled (with meds) Hypertension

Assessed with patient Hx
Will ascertain physician assent
To ensure safety as solriamfetol is contraindicated in patients with these disorders

Planning to become pregnant, pregnant, and/or breastfeeding

Assessed with patient Hx (will ensure use of birth control methods on the screening form)
To ensure safety as solriamfetol has not been demonstrated to be safe for use while pregnant and/or breast feeding.

Unstable medical or psychiatric illness

Assessed with the patient Hx, PHQ-9, and the GAD-7
Assessed with a History and Physical, an EKG, and a clinical chemistries panel
To ensure that the insomnia is not comorbid with unstable medical or psychiatric illness (e.g., Bipolar Disorder)

Symptoms suggestive of sleep disorders other than insomnia

Assessed with the Sleep Disorders Symptoms Checklist (SDS-CL).
To ensure that the insomnia is not comorbid with other intrinsic sleep disorders

Polysomnographic data indicating sleep disorders other than insomnia

Assessed with Home Sleep Apnea Testing (HSAT, type 3 or 4 sleep study).
Subjects w/ an AI of >10 are excluded from the study

Subjects w/ an abnormal Home Sleep Apnea Testing (HSAT, type 3 or 4 sleep study) are excluded from the study
To ensure that the insomnia is not comorbid with other intrinsic sleep disorders.

Evidence of active illicit substance use, abuse, or dependence

Assessed with the patient Hx
Assessed with the AUDIT and CAGE
To ensure that the insomnia is not comorbid with alcoholism or substance abuse

Use of CNS active medications that are for treatment of insomnia or are thought to have caused insomnia as a side effect

Assessed by self-report

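### The examination, EKG and chemistries that 6.b requires are not scheduled in 8.a or 9, and neither is any blood pressure, pulse or on-treatment GAD-7 measurement

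*Combined protocol and SAP*

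**What the plan says.** **Eligibility.** For unstable medical or psychiatric illness, section 6.b gives two lines of assessment: "Assessed with the patient Hx, PHQ-9, and the GAD-7" and "Assessed with a History and Physical, an EKG, and a clinical chemistries panel".

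**Procedures.** The screening list in 8.a has five items: consent, questionnaires, diaries ("Two weeks of prospective assessment with sleep diaries"), PCP assent and the home sleep test. Section 9 then reads:
- 9.a: "Medical Record Review N/A"
- 9.b: "Physical Examination N/A. Physician Assent will be ascertained"
- 9.c: "Vital Signs N/A. Physician Assent will be ascertained"
- 9.d: "The primary lab evaluation at screening is the Home Sleep Apnea Testing"

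**Assent.** Under 5.1, "participants will provide physician assent to confirm eligibility". Section 6.b requires it before enrolment. No section says what it must contain, how recent the information must be, or whether results reach the study team.

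**Drug risk and monitoring.** Section 14.dd says solriamfetol can raise blood pressure and heart rate; the mitigation it gives is physician assent and exclusion of subjects with the relevant diagnoses. Section 9.j relies on the daily diary and a weekly symptom checklist. Section 10.n.iv counts as an adverse event an above-threshold ESS, PHQ-9 or GAD-7, or a 20% rise in the symptom checklist.

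**The concern.** Three gaps affect how safely and consistently subjects are enrolled and followed.

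- **Work-up.** A coordinator following 6.b would wait for an examination, an EKG and a chemistries result. One following 8.a and 9 would proceed on an assent of unspecified content. Stability would then be judged on different information from one subject to the next.
- **Blood pressure and pulse.** The plan names a cardiovascular effect of the drug but schedules no measurement of it. The stated mitigation acts only before enrolment. A rise without symptoms would not be picked up systematically and could not be compared between drug and placebo.
- **GAD-7.** An adverse-event rule that depends on a score cannot be triggered in weeks when the score is not collected. Anxiety is among the side effects listed in 14.dd.

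**Working it through.** The plan gives no figure to reproduce here. The check sets the sections side by side and then works out when a reading would be informative.

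**Step 1: where each 6.b assessment appears elsewhere**

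| 6.b item | 8.a | 9.a-9.d | Elsewhere |
|---|---|---|---|
| History and physical | not listed | examination left to assent | patient history used for other exclusions; no examination named |
| EKG | not listed | not listed | one channel of the sleep-study montage in 5.1 |
| Chemistries panel | not listed | only the sleep test named | blood draw is printed in the section 8 checklist; its tick cannot be read |

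None of the three is an item in 8.a or 9. The montage EKG belongs to a study done to rule out occult sleep disorders and is not linked to the medical screen. A ticked blood-draw box would still leave 8.a and 9.d without a panel.

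**Step 2: scheduled blood pressure or pulse readings.** The 15-row Table of Instruments and 9.j contain diaries, questionnaires, momentary assessment and a vigilance test. Count across screening, 8 treatment weeks and follow-up: 0.

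**Step 3: adverse-event triggers in 10.n.iv.** There are four: ESS, PHQ-9, GAD-7 and the symptom checklist. The table marks ESS, PHQ-9 and the checklist weekly. GAD-7 is in 0 of the 15 rows and is not among the 8 weekly instruments in section 4 (ISI, ESS, PHQ-9, FACIT-Fatigue, PROMIS, BFI, MITAS, FOSQ-10). So 3 of 4 have a weekly schedule.

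**Step 4: when a reading would be informative.** Inputs from 2.2: Tmax about 2 h (range 1.25-3.0 h), half-life 7.1 h. One-compartment oral model at steady state, dosing every 24 h:

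C(t) ∝ exp(-ke·t)/(1 - exp(-24ke)) - exp(-ka·t)/(1 - exp(-24ka)), with ke = ln2/7.1 = 0.0976 per h and ka solved from Tmax = ln(ka/ke)/(ka - ke).

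Level as % of peak, for Tmax 1.25 / 2.0 / 3.0 h:

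| Time after 2pm dose | No lag | Assumed 1 h lag (over-encapsulation) |
|---|---|---|
| 2 h | 96 / 100 / 96 | 99 / 90 / 75 |
| 4 h | 79 / 87 / 96 | 87 / 95 / 100 |
| 19 h (9am) | 18 / 20 / 24 | 20 / 22 / 26 |
| 22 h (noon) | 14 / 15 / 18 | 15 / 17 / 19 |

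A reading 2-4 h after the dose sees 79-100% of peak (75-100% with the lag). A next-morning reading sees 14-24% (15-26%).

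**Step 5: time left to act.** With day 1 the first run-in capsule, run-in is days 1-7 and active drug days 8-35. A reading by day 14 leaves days 15-35, which is 21 of 28 active days.

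**The case against.** The strongest reply is that nothing conflicts. Section 9 does not simply waive examination and vital signs; it assigns them to physician assent. If the subject's physician does the work-up and then assents, both 6.b and 9 are met. Section 9.d calls the sleep test the primary laboratory evaluation, not the only one, and having no record review does not stop staff receiving a letter. This stands. A reader might infer that 6.b and 9 cannot both be followed, or that no chemistries or EKG will be done; the text does not show either. What remains is that no section requires the assent to rest on the 6.b work-up. Within 6.b, the renal, MAOI and coronary/hypertension exclusions name assent as their basis, while this item names tests.

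On monitoring, the plan has more than the diary and checklist. The first five subjects are enrolled slowly (sections 2 and 4), subjects are evaluated monthly when blister packs are returned (section 2), a collaborating physician monitors (11.w), and examination is allowed where appropriate (11.q). The drug is approved, given at the lower of its two tablet strengths for four weeks, with uncontrolled hypertension and major coronary disease excluded. These points lower the risk. None is a scheduled reading, and subject contact is by phone, email and video (8.g).

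On GAD-7, spontaneous complaints and new or worsening symptoms still count as adverse events, so reported anxiety is captured. The table also omits other named instruments, so its silence shows no listed schedule, not that GAD-7 is never given.

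**Conclusion.** The point holds as a change the plan should make, with medium confidence. All three 6.b assessments are absent from 8.a and 9, scheduled blood pressure or pulse readings number 0, and one of four instrument-based adverse-event triggers has no listed on-treatment collection.

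Two stronger inferences are not supported. The renal, coronary and hypertension exclusions are not part of the mismatch, because 6.b itself rests them on history and assent. Nor do the documents show that subjects will come to harm: they give no effect size or standard deviation for blood pressure or pulse. The drug-level figures only time the proposed reading, and they assume that the effect follows drug level. The 1 h lag is also an assumption; section 7.e says only that over-encapsulation may slow absorption.

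**What to change.** 1. **Work-up.** In 8.a and 9.b-9.d, state that assent must document the 6.b work-up: history and physical with blood pressure and pulse, EKG, and chemistries. Accept recent results from the subject's own physician within a window set by the collaborating physician. Say whether the sleep-study EKG channel counts.
2. **Readings.** In all arms, take a cuff blood pressure and pulse reading during the placebo run-in (days 1-7) and again in the first active week (days 8-14), by the same method and 2-4 h after the actual dose, since dosing may move to 1pm or 12pm. A home or pharmacy cuff suits remote conduct. Set an action limit in advance. Add a descriptive drug-versus-placebo summary of change to 10.n.iv, for safety only. With so few subjects it will be imprecise, and a rise that first appears after day 14 could still be missed.
3. **GAD-7.** Add it to the Pre, Weekly and Post schedule, or remove it from the adverse-event rule.

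**Cost.** The work-up is already required by 6.b. If assent alone is current practice, it adds up to three assessments per subject: 60 × 3 = 180 for the 60 recruited, or 60 × 2 = 120 if the sleep-study EKG is accepted. Recent physician results would lower this, and subjects who then fail screening would add to it. The readings number 2 × 40 = 80 to 2 × 60 = 120. GAD-7 is one brief questionnaire at up to 1 + 8 + 1 = 10 time points per subject, or a wording change.
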